8.1.3.1.3 Liver Safety Required Actions and Follow-Up

Table 17 Required Actions and Follow-Up Assessments Following ANY Liver Stopping Event

Actions	Follow-Up Assessments

 • Immediately discontinue study treatments • Report the event to the sponsor within 24 hrs • Complete the liver event eCRF and complete an SAE data collection tool if the event also meets the criteria for an SAE² • Perform liver event follow-up assessments • Monitor the subject until liver chemistries resolve, stabilize, or return to within baseline (see MONITORING below) • Do not restart/rechallenge subject with study treatment unless allowed per protocol and the sponsor Medical Governance approval is granted (refer to Appendix 18) 	
 • Viral hepatitis serology¹ • Only in those with underlying chronic hepatitis B at study entry (identified by positive hepatitis B surface antigen) quantitative hepatitis B DNA and hepatitis delta antibody³. • Blood sample for PK analysis, obtained 24-72 hrs after last dose⁴ • Serum creatine phosphokinase and lactate dehydrogenase. • Fractionate bilirubin, if total bilirubin ≥2xULN • Obtain complete blood count with differential to assess eosinophilia • Record the appearance or worsening of clinical symptoms of liver injury, or hypersensitivity, on the AE eCRF • Record use of concomitant medications on the concomitant medications report


• If restart/rechallenge not allowed per protocol or not granted, permanently discontinue study treatments and may continue subject in the study for any protocol specified follow-up assessments 
MONITORING:
 
For bilirubin or INR criteria:
 
• Repeat liver chemistries (include ALT, AST, alkaline phosphatase, bilirubin) and perform liver event follow-up assessments within 24 hrs• Monitor subjects twice weekly until liver chemistries resolve, stabilize or return to within baseline• A specialist or hepatology consultation is recommended 
For All other criteria:
 
Repeat liver chemistries (include ALT, AST, alkaline phosphatase, bilirubin) and perform liver event follow-up assessments within 24-72 hrs
 
• Monitor subjects weekly until liver chemistries resolve, stabilize or return to within baseline	
form including acetaminophen, herbal remedies, other OTC medications
 
• Record alcohol use on the liver event alcohol intake eCRF 
For bilirubin or INR criteria:
 
• Anti-nuclear antibody, anti-smooth muscle antibody, Type 1 anti-liver kidney microsomal antibodies, and quantitative total immunoglobulin G (IgG or gamma globulins).• Serum acetaminophen adduct HPLC assay (quantifies potential acetaminophen contribution to liver injury in subjects with definite or likely acetaminophen use in the preceding week [James, 2009]).• Liver imaging (ultrasound, MRI or CT) and /or liver biopsy to evaluate liver disease: complete Liver Imaging and/or Liver Biopsy eCRF.
--	---

Abbreviations: AE, adverse event; ALT, alanine aminotransferase; AST, aspartate aminotransferase; CT, computed tomography; DNA, deoxyribonucleic acid; eCRF, electronic case report form; HPLC, high performance liquid chromatography; hrs, hours; IgG, Immunoglobulin G; IgM, Immunoglobulin M; INR, international normalization ratio; MRI, magnetic resonance imaging; OTC, over-the-counter; PCR, polymerase chain reaction; PK, pharmacokinetic; RNA, ribonucleic acid; SAE, serious adverse event; SRM, study reference manual; ULN, upper limit of normal

1. Includes: Hepatitis A IgM antibody; Hepatitis B surface antigen and Hepatitis B Core Antibody (IgM); Hepatitis C RNA; Cytomegalovirus IgM antibody; Epstein-Barr viral capsid antigen IgM antibody (or if unavailable, obtain heterophile antibody or monospot testing); Hepatitis E IgM antibody.
2. All events of ALT $\geq 3 \times \text{ULN}$ **and** bilirubin $\geq 2 \times \text{ULN}$ (>35% direct bilirubin) or ALT $\geq 3 \times \text{ULN}$ **and** INR >1.5, if INR measured which may indicate severe liver injury (possible 'Hy's Law'), **must be reported as an SAE (excluding studies of hepatic impairment or cirrhosis)**; INR measurement is not required and the threshold value stated will not apply to subjects receiving anticoagulants
3. If hepatitis delta antibody assay cannot be performed, it can be replaced with a PCR of hepatitis D RNA virus (where needed) [Le Gal, 2005].
4. PK sample may not be required for subjects known to be receiving placebo or non-sponsor comparator treatments.) Record the date/time of the PK blood sample draw and the date/time of the last dose of study treatment prior to blood sample draw on the eCRF. If the date or time of the last dose is unclear, provide the subject's best approximation. If the date/time of the last dose cannot be approximated OR a PK sample cannot be collected in the time period indicated above, do not obtain a PK sample. Instructions for sample handling and shipping are in the SRM.

Table 18 Liver Chemistry Increased Monitoring Criteria with Continued Therapy

Criteria	Actions

Subject with entry criteria ALT≤2.5xULN ALT ≥3xULN but <5xULN and bilirubin <2xULN, without symptoms believed to be related to liver injury or hypersensitivity and who can be monitored weekly for 4 weeks
 
Subject with documented liver metastases/tumor infiltration at baseline AND entry criteria ALT>2.5xULN but ≤5xULN ALT ≥3xULN and 1.5x baseline value but ALT <5xULN and 2x baseline value and bilirubin <2xULN, without symptoms believed to be related to liver injury, or hypersensitivity and who can be monitored weekly for 4 weeks
	
 • Notify the Medical Lead within 24 hrs of learning of the abnormality to discuss subject safety. • Subject can continue study treatments • Subject must return weekly for repeat liver chemistries (ALT, AST, alkaline phosphatase, bilirubin) until they resolve, stabilise or return to within baseline • If at any time subject meets the liver chemistry stopping criteria, proceed as described above 
For subjects with entry criteria ALT≤2.5xULN
 
 • If, after 4 weeks of monitoring, ALT <3xULN and bilirubin <2xULN, monitor subjects twice monthly until liver chemistries normalize or return to within baseline. 
For subjects with documented liver metastases/tumor infiltration at baseline AND entry criteria ALT>2.5xULN but ≤5xULN
 
If, after 4 weeks of monitoring, ALT <3xULN and <1.5x baseline value, and bilirubin <2xULN, monitor subjects twice monthly until liver chemistries normalize or return to within baseline

Refer to [Appendix 18](#) for liver safety drug restart or rechallenge guidelines.

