8.1.3 Hepatobiliary Events

8.1.3.1 Liver Chemistry Stopping Criteria

Liver chemistry stopping and increased monitoring criteria have been designed to assure subject safety and evaluate liver event etiology in alignment with the FDA premarketing clinical liver safety guidance

fda.gov/downloads/Drugs/GuidanceComplianceRegulatoryInformation/Guidances/UCM174090.pdf

8.1.3.1.1 Liver Chemistry Stopping and Increased Monitoring Algorithm for Subjects WITH entry criteria ALT ≤2.5xULN

[figure not shown]

Table 15 Liver Chemistry Stopping Criteria – Liver Stopping Event for Subjects WITH Entry Criteria ALT≤2.5xULN

ALT-absolute	ALT ≥5xULN
ALT Increase	ALT ≥3xULN persists for ≥4 weeks
Bilirubin^{1,2}	ALT ≥3xULN and bilirubin ≥2xULN (>35% direct bilirubin)
INR²	ALT ≥3xULN and INR>1.5, if INR measured
Cannot Monitor	ALT ≥3xULN and cannot be monitored weekly for 4 weeks
Symptomatic³	ALT ≥3xULN associated with symptoms (new or worsening) believed to be related to liver injury or hypersensitivity

Abbreviations: ALT, alanine aminotransferase; INR, international normalization ratio; ULN, upper limit of normal

1. Serum bilirubin fractionation should be performed if testing is available. If serum bilirubin fractionation is not immediately available, discontinue study treatment for that subject if ALT ≥3xULN **and** bilirubin ≥2xULN. Additionally, if serum bilirubin fractionation testing is unavailable, **record presence of detectable urinary bilirubin on dipstick**, indicating direct bilirubin elevations and suggesting liver injury.
2. All events of ALT ≥3xULN **and** bilirubin ≥2xULN (>35% direct bilirubin) or ALT ≥3xULN **and** INR>1.5, if INR measured which may indicate severe liver injury (possible ‘Hy’s Law’), **must be reported as an SAE (excluding studies of hepatic impairment or cirrhosis)**; INR measurement is not required and the threshold value stated will not apply to subjects receiving anticoagulants
3. New or worsening symptoms believed to be related to liver injury (such as fatigue, nausea, vomiting, right upper quadrant pain or tenderness, or jaundice) or believed to be related to hypersensitivity (such as fever, rash or eosinophilia)

8.1.3.1.2 Liver Chemistry Stopping and Increased Monitoring Algorithm including Subjects WITH Documented Liver Metastases/Tumor Infiltration at Baseline AND entry criteria ALT>2.5xULN but ≤5xULN

[figure not shown]

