Table 16 Liver Chemistry Stopping Criteria – Liver Stopping Event: Subjects with Documented Liver Metastases/Tumor Infiltration at Baseline AND Entry Criteria ALT >2.5xULN but ≤5xULN

ALT-absolute	Both ALT ≥5xULN and ≥2x baseline value
ALT Increase	Both ALT ≥3xULN and ≥1.5x baseline value that persists for 4 weeks
Bilirubin^{1, 2}	ALT ≥3xULN and bilirubin ≥2xULN (>35% direct bilirubin)
INR²	ALT ≥3xULN and INR>1.5, if INR measured
Cannot Monitor	Both ALT ≥3xULN and ≥1.5x baseline value that cannot be monitored for 4 weeks
Symptomatic³	Both ALT ≥3xULN and ≥1.5x baseline value associated with symptoms (new or worsening) believed to be related to liver injury or hypersensitivity

Abbreviations: ALT, alanine aminotransferase; INR, international normalization ratio; ULN, upper limit of normal

1. Serum bilirubin fractionation should be performed if testing is available. If serum bilirubin fractionation is not immediately available, discontinue study treatment for that subject if ALT ≥3xULN and bilirubin ≥2xULN. Additionally, if serum bilirubin fractionation testing is unavailable, **record presence of detectable urinary bilirubin on dipstick**, indicating direct bilirubin elevations and suggesting liver injury.
2. All events of ALT ≥3xULN and bilirubin ≥2xULN (>35% direct bilirubin) or ALT ≥3xULN and INR>1.5, if INR measured which may indicate severe liver injury (possible 'Hy's Law'), **must be reported as an SAE (excluding studies of hepatic impairment or cirrhosis)**; INR measurement is not required and the threshold value stated will not apply to subjects receiving anticoagulants
3. New or worsening symptoms believed to be related to liver injury (such as fatigue, nausea, vomiting, right upper quadrant pain or tenderness, or jaundice) or believed to be related to hypersensitivity (such as fever, rash or eosinophilia)

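### Read literally, Table 18's weekly liver monitoring for subjects with liver metastases or tumor infiltration ends at 5xULN, below the 2x-baseline ALT stop in Table 16

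*Protocol*

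**What the plan says.** Three places in Protocol section 8.1.3.1 set the ALT rules for subjects with documented liver metastases or tumor infiltration at baseline and entry ALT above 2.5 and up to 5xULN.

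- **Monitoring (Table 18, second row).** Treatment continues with weekly liver chemistries when "ALT ≥3xULN and 1.5x baseline value but ALT <5xULN and 2x baseline value and bilirubin <2xULN", provided there are no liver or hypersensitivity symptoms and weekly monitoring is possible. The action list includes "Notify the Medical Lead within 24 hrs of learning of the abnormality".
- **Stop on a single value (Table 16, ALT-absolute row).** "Both ALT ≥5xULN and ≥2x baseline value".
- **Stop on persistence or inability to monitor (Table 16).** "Both ALT ≥3xULN and ≥1.5x baseline value that persists for 4 weeks", and "Both ALT ≥3xULN and ≥1.5x baseline value that cannot be monitored for 4 weeks".

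For subjects with entry ALT up to 2.5xULN, the first row of Table 18 is "ALT ≥3xULN but <5xULN and bilirubin <2xULN". The matching ALT-absolute stop in Table 15 starts at 5xULN, and Table 15's cannot-monitor row is "ALT ≥3xULN and cannot be monitored weekly for 4 weeks".

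**The concern.** A monitoring row and its paired stop should meet: close monitoring should continue until the value that stops treatment. For entry ALT up to 2.5xULN they do. In the liver-metastases row the stop is a joint condition (both limits reached), so just below the stop means below one limit *or* below the other. The cell joins the two upper limits with *and*, and the second limit has no comparator. Taken as written, monitoring ends at the lower limit while the stop starts at the higher one.

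At stake are two specific actions, weekly panels and 24-hour notification, for subjects who continue both drugs. They are lost most completely for those with the highest entry ALT.

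**Working it through.** **Inputs.** Entry ALT b in (2.5, 5] xULN; Table 18 lower limits 3xULN and 1.5b, upper limits 5xULN and 2b; Table 16 ALT-absolute limits 5xULN and 2b. All are in section 8.1.3.1. I take baseline to equal entry ALT. The plan states no figure of its own to reproduce.

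**Step 1, literal monitoring band.** It runs from max(3, 1.5b) to below min(5, 2b). Since b > 2.5, 1.5b > 3.75 and 2b > 5, so the band is 1.5b to <5. It is empty when 1.5b ≥ 5, that is from b = 5/1.5 = 3.33. That covers (5 − 3.33)/(5 − 2.5) = two-thirds of the width of the entry range (not of subjects, whose entry values are not given).

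**Step 2, stop.** The ALT-absolute stop is ALT ≥ max(5, 2b) = 2b.

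**Step 3, gap.** Values from max(5, 1.5b) to <2b fall in neither rule. As a share of the range from 1.5b to 2b, the gap is [2b − max(5, 1.5b)]/(0.5b).

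| b (xULN) | Literal weekly band | Stop from | Gap | Share of 1.5b–2b not covered | Band with *or* |
|---|---|---|---|---|---|
| 2.75 | 4.125 to <5 | 5.5 | 5 to <5.5 | 0.5/1.375 = 36% | 4.125 to <5.5 |
| 3 | 4.5 to <5 | 6 | 5 to <6 | 1/1.5 = 67% | 4.5 to <6 |
| 3.5 | none | 7 | 5.25 to <7 | 100% | 5.25 to <7 |
| 4 | none | 8 | 6 to <8 | 100% | 6 to <8 |
| 5 | none | 10 | 7.5 to <10 | 100% | 7.5 to <10 |

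**Step 4, comparison row.** For entry ALT up to 2.5xULN, monitoring is 3 to <5xULN and the stop starts at 5xULN, so the gap is 0.

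**Step 5, check of *or*.** The complement of *both ≥5xULN and ≥2b* is *<5xULN or <2b*, an upper limit of max(5, 2b) = 2b. A grid over ALT 0 to 13xULN and baselines 0.5 to 6xULN shows no gap and no overlap with the ALT-absolute stop. This also covers a Day 1 retest that lowers baseline below 2.5xULN: at baseline 2.4 the literal row ends at 4.8 and the stop starts at 5, and *or* closes that too.

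**Step 6, who could be affected.** The Amendment 11 rationale lists 36 HCL + 10 + 6 glioma + 2 ATC + 1 BTC = 55 on treatment at 06-Apr-2020. Against the entry limits in section 5.4.1, Table 3:
- BTC (1 subject): up to 5xULN with liver metastases, so a candidate. This subject's entry ALT and liver status are not given.
- ASI and MM: same limit, but no subjects on treatment.
- ATC (2): limit 2.5xULN, outside this row.
- Glioma (16): limit 3xULN, and liver metastases would also be needed.
- HCL (36): limit below 5xULN, but footnote 5 requires the elevation to come from hemolysis or hypersplenism without hepatic dysfunction. Documented liver infiltration is unlikely, though the wording does not exclude it.

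**The case against.** The strongest reply is that the literal reading defeats its own row. A row written for entry ALT up to 5xULN cannot have been meant to be unusable from 3.33xULN. The paired limits mirror Table 16, and the natural sense is at or above the first pair and below the paired stop, which gives 1.5b to <2b and no gap. This stands as an account of intent, and it is why the point is a drafting error and not a design choice. It does not make the text safe to leave. The step-down instruction for the same subjects writes its comparators out, "If, after 4 weeks of monitoring, ALT <3xULN and <1.5x baseline value, and bilirubin <2xULN", and there *and* plainly means below both, so a careful site could read the trigger the same way.

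The section 8.1.3.1.2 algorithm for this population is a figure that was not available for this review. It may show the intended limits. If it does, the cell still contradicts it.

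A reader might infer that subjects in the gap are unprotected. The documents do not support that. Table 16's persistence and cannot-monitor rows have no upper ALT limit, and its symptom, bilirubin and INR stops apply. Section 7.4.8 requires significantly abnormal tests to be repeated. Table 11 covers related events without specific guidance and interrupts both drugs for Grade 3 or intolerable Grade 2 events. What none of these gives is a weekly interval: Table 16's cannot-monitor row omits the word *weekly* that Table 15 has, section 7.4.8 names no interval, and Table 11 depends on judged relatedness.

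A reader might also infer a three-week detection delay. Chemistry is scheduled every 4 weeks (section 7.1), so the difference from weekly panels is at most 28 − 7 = 21 days. That extreme assumes no repeat test in between, despite section 7.4.8. A 4-weekly panel still at or above 1.5b would also bring the persistence stop into play.

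**Conclusion.** The point holds as a minor drafting error in an operative safety threshold. Under the literal reading, 36% of the range between 1.5b and 2b lacks a stated weekly interval at b = 2.75xULN, 67% at b = 3, and all of it from b = 3.33. This assumes that baseline equals entry ALT and that the sentence is applied as written. Confidence is medium because the figure is unseen and sites may already read the row as intended.

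At most one subject on treatment at 06-Apr-2020 (1/55 = 1.8%) is a likely candidate. That is an upper bound for the likely group, not an expected count. Adding all HCL subjects gives 37 of 55, but this is only a formal ceiling: footnote 5 of Table 3 makes it implausible as an estimate. The documents show no past event, and no efficacy endpoint or analysis is touched.

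**What to change.** Replace the ALT and bilirubin part of the cell with: *ALT ≥3xULN and ≥1.5x baseline value, but (ALT <5xULN or ALT <2x baseline value), and bilirubin <2xULN*. Keep the symptom and weekly-monitoring conditions that follow. Swapping one word alone is not enough: without the comparators and brackets, the *or* would be ambiguous against the bilirubin condition.

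Check the wording against the section 8.1.3.1.2 figure before issuing it. If the figure already shows 1.5x to <2x baseline, only the table cell needs correcting.

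Leave Table 16 unchanged. Leave the 4-week step-down unchanged too: read literally it requires ALT below 3xULN (since 1.5b > 3.75), which errs towards more monitoring.

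The cost is one table cell, by clarification letter or in the next amendment, and about 3 extra liver panels per 4-week episode (4 weekly instead of 1 scheduled).

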8.2 Dose Modification and Management Guidelines for Events of Special Interest

The severity of AEs will be graded utilizing the CTCAE v4.0 [NCI, 2009]. Brief guidelines for dose modifications and interruptions for management of common toxicities associated with the study treatments are provided in this section.

8.2.1 Dermatological Events

8.2.1.1 Rash

Rash is frequently observed in subjects receiving trametinib, dabrafenib, or the combination of both therapies. Guidelines for management are based on experience with other MEK inhibitors and epidermal growth factor receptor inhibitors [Balagula, 2011; LaCouture, 2011].

The institutional standards for the management of skin-related AEs can differ from these guidelines. In this case, best clinical judgment should be applied and a consultation with the Medical Monitor may be required.

Table 19 Guidelines for Supportive Care of Rash

Type of Care	Action
Prevention/Prophylaxis ¹	
 • Avoid unnecessary exposure to sunlight • Apply broad-spectrum sunscreen (containing titanium dioxide or zinc oxide) with a skin protection factor (SPF) ≥15 at least BID. • Use thick, alcohol-free emollient cream (e.g., glycerine and cetomacrogol cream) on dry areas of the body at least BID. • Topical steroids and antibiotics should be applied at least BID starting on Day 1 of study treatment, to body areas such as face, chest, and upper back. 
 • Use mild-strength topical steroid (hydrocortisone 1% cream) or 
 • topical antibiotic (e.g., clindamycin) or oral antibiotics (e.g., doxycycline 100 mg BID, minocycline 100 mg BID)
Symptomatic Care ²	
 • Pruritic lesions: cool compresses and oral antihistamine therapies • Fissuring lesions: Monsel's solution, silver nitrate, or zinc oxide cream • Desquamation: thick emollients and mild soap • Paronychia: antiseptic bath, local potent corticosteroids in addition to oral antibiotics; if no improvement, consult dermatologist or surgeon • Infected lesions: appropriate bacterial/fungal culture-driven systemic or topical antibiotics

Abbreviations: BID, twice daily; SPF, sun protection factor

1. Rash prophylaxis is recommended for the first 6 weeks of study treatment
2. Subjects who develop rash/skin toxicities should be seen by a qualified physician and should receive evaluation for symptomatic/supportive care management

Guidelines for management and dose reduction for rash considered to be related to study treatment are provided in Table 20.

Table 20 Management and Dose Modification Guidelines for Rash

CTCAE Grade	Adverse Event Management	Action and Dose Modification
Grade 1	
 • Initiate prophylactic and symptomatic treatment measures¹ • Use moderate strength topical steroid² 
Reassess after 2 weeks
	
 • Continue study treatment • If rash does not recover to baseline within 2 weeks despite best supportive care, reduce trametinib by one dose level³
Grade 2	
 • Initiate prophylactic and symptomatic treatment measures • Use moderate strength topical steroid² 
Reassess after 2 weeks
	
 • Reduce study treatment by one dose level 
 • If rash recovers to ≤Grade 1 within 2 weeks, increase dose to previous dose level

CTCAE Grade	Adverse Event Management	Action and Dose Modification
		
 • If no recovery to ≤Grade 1 within 2 weeks, interrupt study treatment until recovery to ≤Grade 1 • Restart study treatment at reduced dose level³
Grade ≥3	
 • Use moderate strength topical steroids² PLUS oral methyl-prednisolone dose pack • Consult dermatologist 	
 • Interrupt study treatment until rash recovers to Grade ≤1 • Restart³ with study treatment reduced by one dose level⁴ • If no recovery to Grade ≤2 within 4 weeks, permanently discontinue study treatment.

Abbreviations: CTCAE, Common Terminology Criteria for Adverse Events

1. Rash prophylaxis is recommended for the first 6 weeks of study treatment
2. Moderate-strength topical steroids: hydrocortisone 2.5% cream or fluticasone propionate 0.5% cream
3. Approval of the Medical Lead is required to restart study treatment after >4 weeks of interruption.
4. Escalation of study treatment to previous dose level may be considered if no rash is evident 4 weeks after restarting study treatment

8.2.1.2 Palmar-plantar Erythrodysesthesia

Palmar-plantar erythrodysesthesia (PPE) syndrome: Measures for PPE syndrome should include lifestyle modification (avoidance of hot water, traumatic activity, constrictive footwear, or excessive friction on the skin and the use of thick cotton socks and gloves, and shoes with padded insoles) and symptomatic treatments. Apply moisturizing creams frequently, topical keratolytics (e.g., urea 20 to 40% cream, salicylic acid 6%, tazarotene 0.1% cream, fluorouracil 5% cream), clobetasol propionate 0.05% ointment for erythematous areas, topical lidocaine 2%, and/or systemic pain medication such as nonsteroidal anti-inflammatory drugs, codeine, and pregabalin for pain. Dose modification may also be required.

8.2.1.3 SCARs (Severe Cutaneous Adverse Reactions)

Cases of severe cutaneous adverse reactions (SCARs), including Stevens-Johnson syndrome, and drug reaction with eosinophilia and systemic symptoms (DRESS), which can be life-threatening or fatal, have been reported during treatment with dabrafenib in combination with trametinib. Before initiating treatment, patients should be advised of the signs and symptoms and monitored closely for skin reactions. If signs and symptoms suggestive of SCARs appear, dabrafenib and trametinib should be permanently discontinued.

